The method of ESIN was introduced in the 1970s using Kirschner wires. In the 1990s ESIN specific implants became widely available. ESIN has since shown to produce excellent results with few complications [4,19]. Advantages include closed fracture reduction, minimal soft tissue dissection, early motion, sustained reduction and easy hardware removal. Complications are rare but do exist in the form of soft tissue irritation, superficial radial nerve injury, extensor pollicis longus tendon rupture, delayed union, malunion, refractures and infection [3,20,21].

Several metallic alloys have been used to produce ESIN implants. The most widely used is titanium (Ti6Al14V) which has suitable elastic properties [4]. The Titanium Elastic Nail System (DePuy Synthes, Raynham, Massachusetts, USA) is commonly used and has been used in our institution for several years.

Hardware removal

Removal of metal implants including ESIN after fracture surgery in children is currently the practice in Denmark and is sanctioned by the Danish Health Authority. Implant removal is done because of potential interference with the child's growing skeleton, late tissue reactions, difficulty in late removal and concerns about stress shielding due to metal stiffness [22].

Bioabsorbable implants

It is important to retain a common and unified nomenclature within this research field. Liu et al. [23] suggest that foreign implants or other kinds of biomaterials eventually absorbed by the body be labeled as "absorbable" or with the prefix "bio". The term "absorbable" focuses on the host's metabolism of degraded products of the implanted material. Within this study protocol and the final manuscript, we will adhere to the label "bioabsorbable implants".

Bioabsorbable implants have been known since the 1970s and over the years many different materials have been investigated. The use of bioabsorbable implants is increasing and has proved a safe and feasible method of stabilizing fractures in the growing skeleton [24–26]. By using bioabsorbable implants the need for implant removal is overcome and risks of late tissue reactions, stress shielding and infections are lowered [27].

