Implants made from oriented poly L-lactide-co-glycolide (PLGA) copolymers are strong enough to support fractured bones. The monomers of PLGA are L-lactic acid and glycolic acid, which are part of the normal metabolic chemistry of human cells. PLGA implants undergo a controlled degradation through hydrolysis forming lactic acid and glycolic acid which are absorbed by the cells and metabolized into carbon dioxide and water. The implant retains strength and size for at least eight weeks and over the course of approximately two years the implant will be completely absorbed [28]. Medical grade PLGA implants manufactured by Bioretec Ltd. ([name]) are sterilized with gamma radiation. Gamma radiation also reduces molecular weight of oriented PLGA implants. The reliability and safety of the Activa IM-Nail[™] has been described in the manufacturer's premarket trials and one RCT [7], the implant is FDA and CE approved for the same purpose as in the present study.

Objectives

Primary objective

The primary objective of this study is to evaluate the amount of radiological healing three months after surgery with the Activa IM-Nail[™] for pediatric diaphyseal forearm fractures.

Secondary objectives

The secondary objectives are to report the functional outcome, calculate refracture rate and any other complications up to two years following surgery and to describe MRI findings two years after insertion of Activa IM-Nail™.

Hypothesis

We hypothesize that radiological healing is established three months after surgery with the Activa IM-Nail™.

Methods and materials

Study design

We use a cohort study design [29] conformed to the STROBE Statement [30]. We aim to recruit all children with diaphyseal forearm fractures (cohort) operated with BIN (exposure) and report radiological healing

(outcome). This study design is relevant in reporting radiological healing and calculating absolute risk of adverse events based on the exposure in our cohort.

Selection and withdrawal of participants

Setting

The study will be performed in the Capital Region of Denmark, Europe. Patients in Herlev and Gentofte University Hospital's catchment area (population 700.000 of which 80.000 are children age 3-15) are eligible for recruitment.

Participants

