Children are not able to give informed consent to participate in a study. Therefore, all legal guardians are asked to consent on behalf of the child. Oral and written information about the study, together with general information about participating in a research project from the Danish National Committee on Health Research Ethics is given face-to-face by the PI prior to asking for consent. Information is given in an undisturbed environment at the pediatric ward. The PI is the head of pediatric orthopedic trauma and is very skilled in communication with both parents and injured children.

Unstable or displaced diaphyseal forearm fractures usually do not require emergent treatment, but we strive to treat fractures as soon as possible. In planning, both surgeons and operating personnel need time to prepare for the specific procedure. Therefore, we ask that consent is given the day before surgery at the latest. Parents will in most cases have at least 24 hours to consider enrollment however, there might be factors (e.g. open fracture or neurovascular compromise) that dictate more emergent treatment requiring consent with less consideration time.

If participation is declined the patient will receive standard treatment with TEN, and standard rehabilitation and follow-up after 2 and 6 weeks and 6 months. TEN will be removed approximately 6 months after insertion during a scheduled outpatient operation under general anesthesia.

Follow-up

Outpatient visits are scheduled at 2 and 6 weeks, 3 and 6 months and 1 and 2 years following surgery.

All participants live in the catchment area of our hospital with short transportation time. Information about the time and place for the follow-up examination is sent via the electronic health record (EHR) and physically by mail to the current address registered in the Civil Registration System. Parents are usually very keen to take their children for follow-up appointments making the risk of missing an appointment low. Any participants who miss an appointment will be contacted by phone to reschedule.

Withdrawal

If a participant chooses to discontinue the follow-up examinations for any reason, the date and reason for drop-out is recorded and the latest examination will be carried forward in the analysis. In case of reoperation, the patients continue with their follow-up examinations and they are included in the 2-year analysis. In case of drop-out before the first follow-up visit the participant will be excluded from the

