Studies have shown a 5% risk of nerve injury [32], however all cases had spontaneous recovery of nerve function.

Extra visits to the outpatient clinic

We follow all patients with six visits to the outpatient clinic. This is three more than with standard treatment and might be viewed as a disadvantage.

Radiation

Three extra radiographs are obtained during outpatient visits. A radiograph of an extremity leads to a radiation dose of less than 0.001 mSv and compares to 3 hours of background radiation. Three extra radiographs is far below the threshold of 0.1 mSv.

MRI

Two years after surgery an MRI is performed. We follow a special MRI-protocol without the need for sedation or anesthesia.

Variables

At recruitment baseline data will be collected:

- Demographic data (age, gender, handedness, height and weight)
- Injury data (date and time, left or right arm, location, activity, mechanism, open or closed fracture, diagnosis code, indication for surgery)
- Historical data (metabolic disease, medication, other systemic illness)

After surgery, operative data is collected (date and time of surgery, operative time, closed or open reduction, any complications).

During follow-up in the outpatient clinic data will be collected on:

- Pain (Faces Pain Scale Revised) or VAS according to child's age
- Use of pain medication
- Wound appearance (visible signs of infection)
- Neurovascular status
- Bilateral elbow and forearm range of motion (ROM) measured in degrees by goniometer
- Forearm radiographs in AP and ML planes (Radiographic Union Score)

2 years following surgery MRI findings (absorption of the nail, activity at fracture site, soft-tissue reactions) will be collected.

Outcomes

The primary objective is quantified using the Radiographic Union Scale (RUS) [33] based on degree of callus formation and visibility of fracture line on AP and ML plain radiographs. We define established healing as a RUS of > 9.

Secondary objectives are described as absolute risk of refracture, time to established healing (weeks), pain (Faces Pain Scale – Revised (FPS-R) or visual analogue scale (VAS)), elbow and forearm range of motion (in degrees), visible signs of infection, neurovascular complications and any reoperation. MRI findings (absorption of the nail, activity at fracture site, soft-tissue reactions) after 2 years are described.

The Radiographic Union Score

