Consent gives the person responsible for the trial and the relevant authorities direct access to obtain information in the patient's medical record for the purpose of carrying out the project as well as for control purposes.

Data security

The patient's hospital records are stored securely in the hospital's EHR (Epic Systems Corporation, Verona, Wisconsin, USA).

The project's Electronic Case Report Form (eCRF) is stored securely using Research Electronic Data Capture (RedCAP, Vanderbilt University, USA).

Radiographs and MRIs are stored in the hospital's Picture archiving and communication system (PACS).

The project complies with the EU's General Data Protection Regulation (GDPR) according to the Danish law on data protection *Databeskyttelsesloven* and *Databeskyttelsesforordningen*.

Publication

The study will be reported to ClinicalTrials.gov before trial initiation.

The results, both positive, negative and inconclusive, will be sent for submission in a peer reviewed international orthopedic journal, and the results will be presented at national and international scientific meetings. Reporting will adhere to the STROBE guidelines for cohort studies [30].

Perspective

If proven safe and effective, the use of BIN would deem hardware removal unnecessary and relieve the child of further surgery and reduce the healthcare costs.

This study is a pilot for a randomized controlled trial comparing the Activa IM-Nail[™] (Bioretec Ltd., [name]) to the Titanium Elastic Nail System (TEN) (Depuy Synthes, Raynham, Massachusetts, USA) which is currently used for pediatric forearm fractures in our hospital. This pilot study will diminish any learning curve, evaluate the clinical safety of the implant, and test the recruiting and follow-up of patients before embarking on the RCT.

Disclosures and economy

The initiative for this study has been taken solely by the authors.

The authors and affiliated colleagues have not received any financial payments or other benefits from any commercial entity related to the subject of this study. The authors declare that they have no conflict of interest.

Participants do not receive any economic benefits or gifts from the participation in this project.

Literature

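### Soft-tissue reaction is a named variable only on the 2-year MRI; before then its capture rests on undefined, unprompted complication reporting, and a sterile reaction may be counted as a sign of infection

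*Combined protocol and SAP*

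**What the plan says.** Soft-tissue reaction appears as a study variable in one place, the last line of the protocol's Variables section: "2 years following surgery MRI findings (absorption of the nail, activity at fracture site, soft-tissue reactions) will be collected". The Outcomes section repeats it in the same form: "MRI findings (absorption of the nail, activity at fracture site, soft-tissue reactions) after 2 years are described".

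The visit schedule, under Follow-up, reads: "Outpatient visits are scheduled at 2 and 6 weeks, 3 and 6 months and 1 and 2 years following surgery". The data listed for those visits are pain, pain medication, wound appearance, neurovascular status, range of motion and radiographs. The only entry about the local soft tissues is "Wound appearance (visible signs of infection", and visible infection is then carried into Outcomes as a secondary outcome with no further criterion. The list of operative data includes complications; the list for visits does not.

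On timing, the Bioabsorbable implants section says that the nail keeps its strength and size for eight weeks or more, and that "over the course of approximately two years the implant will be completely absorbed".

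Three places promise general safety reporting. The Abstract covers adverse events during follow-up, the Secondary objectives cover further complications through two years, and Statistics counts complications. None defines or grades these events or links them to a visit item. The Ethics section adds an interim analysis, six months after the last patient is recruited, to look for side effects not known beforehand.

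**The concern.** Tissue reaction and infection are two of the risks on which the protocol rests its case for this class of implant. The Bioabsorbable implants section says that the "risks of late tissue reactions, stress shielding and infections are lowered". The Perspective section says that the pilot will "evaluate the clinical safety of the implant" before a randomised trial. A pilot with that purpose should be able to say how many children had a local reaction to the nail and how many had an infection, and to tell the two apart.

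As listed, the variables do not do this reliably. The one dedicated look for tissue reaction is a single image at about the expected end of absorption. At every visit before it, the only prompt about the local soft tissues asks about infection. A reaction that comes and goes in between is not systematically sought, and if it is visible at an entry site the form's wording points towards infection. Both figures would then go into the planning of the randomised trial with an unknown error.

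**Working it through.** The plan gives no rate or calculation on this point, so there is no figure to reproduce. The check sets the sections side by side and adds simple timeline arithmetic.

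**1. Where a sterile local reaction could be recorded**

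| Protocol section | What is recorded | When |
|---|---|---|
| Variables, operative data | complications, unspecified | at surgery |
| Variables, visits | pain, pain medication, wound (as infection), neurovascular status, range of motion, radiographs | each visit |
| Variables and Outcomes, MRI | soft-tissue reaction, by name | 2 years |
| Outcomes, clinical | refracture, infection signs, neurovascular complications, reoperation, pain, range of motion | during follow-up |
| Abstract, Secondary objectives, Statistics | complications and adverse events, undefined | to 2 years |

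Only the MRI row names the event. The last row would admit it but does not prompt for it. Items such as "Pain (Faces Pain Scale Revised) or VAS according to child's age", range of motion and reoperation may signal a problem without identifying its cause.

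**2. Visits before the MRI**

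Six visits are scheduled and one coincides with the MRI, so 6 − 1 = 5 come before it. Three of those (3 months, 6 months, 1 year) fall after the eight weeks for which the nail is said to keep its size and strength. None of the five has a listed tissue-reaction item. Between the 1-year and 2-year visits there are 24 − 12 = 12 months with no visit.

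**3. What the interim analysis would hold**

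Inputs: estimated recruitment of 12 months (Recruitment); analysis 6 months after the last recruitment (Ethics); MRI at 24 months. Surgery is taken to follow recruitment closely.

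- Time of the interim analysis from the first patient: 12 + 6 = 18 months.
- Follow-up of the first patient: 18 − 0 = 18 months. Follow-up of the last: 18 − 12 = 6 months.
- First 2-year MRI: month 24, which is 24 − 18 = 6 months after the interim analysis.
- For even one MRI to exist by then, recruitment of R months would need R + 6 ≥ 24, that is R ≥ 18.

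On the plan's own estimate, the interim analysis has no dedicated tissue-reaction data.

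**4. What one child does to the results**

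Take a child with sterile swelling at an entry site at 6 months that has settled by 1 year. There are three possible records:

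- it is volunteered as a complication, and is counted but without a defined category;
- it is entered as a visible sign of infection, so infection rises by one and tissue reaction does not;
- it is not recorded, so tissue reaction is short by one.

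Each child is 1/30 = 0.033, or 3.3 percentage points.

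**5. Drop-outs**

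The Withdrawal section carries the latest examination forward. The MRI is done once, so a child who leaves before 2 years has no earlier MRI to carry and contributes no dedicated tissue-reaction data.

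**The case against.** The strongest reply is that the plan already covers such events. Its secondary objectives take in further complications through two years, the Abstract promises adverse events, Statistics counts complications, and reoperation is an outcome. Nothing limits these to severe events. This stands to the extent that a sterile reaction can be recorded. A reader might infer from the visit list that such a reaction must be entered as infection or lost altogether; the documents do not support that. What they lack is a definition, a prompt at the visits, and any rule separating sterile reaction from infection.

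A second reply concerns timing. Absorption is given as approximate and the eight weeks as a minimum. The MRI itself assesses how far the nail has been absorbed, so it may still show a residual or late reaction. That also stands. A reader might infer that the MRI is bound to find nothing, or that reactions are to be expected in a fixed window between eight weeks and two years. The documents give no timing for tissue reactions and describe the degradation products as part of normal metabolism. The point needs only the weaker statement that a reaction which has resolved may not be visible at two years.

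Third, the case report form is not among the documents and may hold more than the Variables section lists. That is possible. The criticism is of the plan as written, and the plan should state the item if it exists.

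Fourth, this is a small, descriptive, single-arm pilot with no comparator, and lower tissue-reaction risk is background rationale, not a hypothesis under test. That limits how much weight the point carries but does not remove it, since evaluating safety is a stated purpose.

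**Conclusion.** The point holds in a limited form. Tissue reaction is specifically sought only once, at about the expected end of absorption. Before then, including at the interim analysis, its capture depends on unprompted reporting under undefined terms. The direction is under-ascertainment of tissue reaction and possible overstatement of infection.

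The size cannot be stated. The documents give no reaction rate, so any assumed number of events would be a guess; all that can be said is that each child moves a proportion by 3.3 points at n = 30. The finding about the interim analysis rests on the estimated 12-month recruitment and would change only if recruitment took 18 months or longer. The reading of the visits rests on the Variables list being a fair summary of the form.

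The primary outcome, radiographic healing at three months, is not affected. This is a gap in safety ascertainment that is worth closing because the remedy is cheap and the information cannot be reliably recovered later.

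**What to change.** At each existing visit from 6 weeks on (6 weeks, 3 months, 6 months, 1 year and 2 years), add an eCRF item for local tissue reaction: swelling, tenderness, sinus or discharge at a nail entry site or along the forearm, each yes or no, with dates of onset and resolution. Ask about the time since the previous visit, so that episodes in the 12-month gap before the last visit are covered.

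Record this separately from the investigator's judgement of whether infection is present, so that the two can be tabulated against each other. The separation should not rely on culture results, because the protocol schedules none.

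Include the item in the interim analysis. Report the cumulative proportion of children with a local tissue reaction to 2 years as a secondary outcome, with the number assessed at each visit. Keep the 2-year MRI as a description of residual findings.

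The cost is a few form fields at examinations that already take place, with no new visit, test or staff. The reported reaction rate may be higher than it would be under the present plan.

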Study protocol - Use of the bioabsorbable Activa IM-Nail™ in pediatric diaphyseal forearm fractures: a cohort study of 30 patients Version 3.5 – May 2021 – Protocol ID: H-21004012

Study protocol

Use of the bioabsorbable Activa IM-Nail[™] in pediatric diaphyseal forearm fractures: a cohort study of 30 patients

[name], [name], [name] and [name]

Herlev and Gentofte University Hospital, Copenhagen, Denmark

The Danish Data Protection Agency ID: P-2020-1197 The Danish National Committee On Health Research Ethics ID: H-21004012

Abstract	3
Introduction	4
Background	4
Epidemiology	4
Treatment options	4
Metal Elastic Stable Intramedullary Nailing (ESIN)	5
Hardware removal	5
Bioabsorbable implants	5
Objectives	6
Primary objective	6
Secondary objectives	6
Hypothesis	6
Methods and materials	6
Study design	6
Selection and withdrawal of participants	7
Surgical technique and post-operative regime	9
Risks, side effects and disadvantages	9
Variables	
Outcomes	11
The Radiographic Union Score	11
Faces Pain Scale – Revised (FPS-R)	11
Visual analogue scale	12
Bias	12
Study size	13
Statistics	13
Discussion	13
	40
Ethics and security	
Ethics	
Identification of the implant	
Hospital records Data security	
Data security	14
Publication	15
Perspective	15
Disclosures and economy	15
Literature	16

Abstract

Background

Pediatric diaphyseal forearm fractures are common and one of the most frequent reasons for orthopedic care. Fractures in need of surgery are often treated with metal Elastic Stable Intramedullary Nails (ESIN). Nail removal after 6-12 months is generally advocated. Surgical hardware removal has few complications; however, it is a substantial burden on the child, the family and healthcare economy. Bioabsorbable Intramedullary Nails (BIN) have been developed for the same indications as metal ESIN. The use of bioabsorbable implants would deem hardware removal unnecessary and relieve the child of further surgery and reduce healthcare costs.

Methods

We aim to recruit all children in the catchment area of Herlev and Gentofte University Hospital (Copenhagen, Denmark) with acute unstable diaphyseal forearm fractures. Participants will be operated with BIN and followed consecutively for 2 years with interim analysis of data after 6 months. We will report radiological healing using the Radiographic Union Score (RUS) 3 months after surgery together with any adverse events during follow-up.

Discussion

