Operative treatment with metal ESIN is the preferred technique for stabilizing pediatric forearm fractures. Removal of the metal nails is generally advocated in many countries including Denmark. By using BIN, a second operation to remove the nails is avoided.

The hypothesis is that satisfactory fracture healing is accomplished 3 months after operation with BIN. The only previous study on BIN used forearm rotation and not fracture healing as primary outcome [7]. The authors describe that all 15 fractures operated with BIN had healed after 2 years.

The cost of one Activa IM-Nail[™] (\$400) is approximately 4 times higher compared with a traditional TEN (\$100). However the cost of implant removal is approximately \$1900 [7,42] and the extra implant costs are readily balanced out.

Ethics and security

Ethics

The implant is CE approved for the same indications as the use in this study. Permission from the Danish Data Protection Agency is obtained before the inclusion is initiated. The trial will be conducted in accordance with the Declaration of Helsinki of 1996 and principles of good clinical practice.

As with any treatment in the Danish healthcare system all patients are insured and covered by The Patient Compensation Association (Patienterstatningen).

To quantify any unknown side effects or complications an interim analysis of data will be performed 6 months after recruitment of the last patient. An absolute refracture rate of more than 25% is not tolerated and will be a criterion for stopping the study.

In comparison with the standard follow up of pediatric forearm fractures there are 3 additional visits to the out-patient clinic with radiographs of the forearm in AP and ML view. Collectively, the effective dosage is 0.003 mSv - far below 0.1 mSv and is considered insignificant.

Identification of the implant

The traceability of the device is identified by device name, catalogue number (REF) and batch number (LOT).

Hospital records

No access to the patient's EHR regarding the study is made before informed consent to participate is given.

In order to plan and conduct visits, admission and operation we ask that consent is given to access the patient's EHR. We ask permission to retrieve patient-related data and to read entries regarding visits, admission and operation. We ask permission to access radiographs and MRIs.

We ask that access the patient's EHR is given until the conclusion of the project.

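### Refracture and reoperation are two-year outcomes, but the protocol states no data item or record search to find them between visits or after drop-out, so the refracture rate may be understated

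*Combined protocol and SAP*

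**What the plan says.** **Outcomes.** The secondary objectives include to "calculate refracture rate and any other complications up to two years following surgery". The Outcomes section repeats this: "Secondary objectives are described as absolute risk of refracture, time to established healing (weeks", and later in the same sentence "visible signs of infection, neurovascular complications and any reoperation". The Abstract promises to report healing "together with any adverse events during follow-up".

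**Data collected.** Under Variables, the list headed "During follow-up in the outpatient clinic data will be collected on" has six entries: pain, pain medication, wound appearance (for infection), neurovascular status, range of motion, and forearm radiographs with the RUS as the named variable. Complications of the operation are recorded with the operative data. Soft-tissue reactions are recorded at the two-year MRI.

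**Timing.** "Outpatient visits are scheduled at 2 and 6 weeks, 3 and 6 months and 1 and 2 years following surgery". A family that misses a visit is phoned to rebook (Follow-up). A child who discontinues has the latest examination carried forward; one who leaves before the first visit is excluded from the analysis; a reoperated child stays in follow-up and in the two-year analysis (Withdrawal).

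**Decision.** Under Ethics, together with the interim analysis six months after the last patient is recruited: "An absolute refracture rate of more than 25% is not tolerated". Exceeding this rate is a criterion for stopping the study.

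**Record access.** Under Hospital records: "We ask permission to retrieve patient-related data and to read entries regarding visits, admission and operation". Access to radiographs and MRIs is also sought, and record access lasts until the project ends.

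**The concern.** The refracture risk is the only outcome with a numerical stopping limit, and the study is meant to assess the implant's safety before a randomized trial. The protocol nevertheless does not say how a refracture enters the dataset. If it happens and is treated between two visits, no listed item asks about it. If it happens after a child stops attending, no stated step looks for it, and the carry-forward rule keeps the child at the last, event-free status. Missed events can only lower the reported rate, which is the unfavourable direction for a safety outcome.

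**Working it through.** **1. Outcomes against data items (Outcomes and Variables sections).**

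| Outcome | Item collected at visits |
|---|---|
| Infection signs | Wound appearance |
| Neurovascular complications | Neurovascular status |
| Refracture | None by name; radiographs, with RUS as the variable |
| Any reoperation | None |
| Any adverse event | No general question; partly covered by the first two rows, the operative data and the two-year MRI |

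The gap is in the last three rows.

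**2. Visit gaps.** From month 6: 12 − 6 = 6 months, then 24 − 12 = 12 months. So 18 of the 24 months lie in two intervals, each closed by one visit.

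**3. What RUS can show.** Each of four cortices scores 1 to 3, so the total runs from 4 to 12, and healing is defined as more than 9. A refracture that has bridged on all four cortices by the next film scores 4 × 3 = 12, the same as a bone that never refractured. A film taken earlier may show the refracture, but the score alone does not identify one.

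**4. The limit as a count.** The study size of 30 is stated without a calculation; it cannot be reproduced and is not disputed here. 25% of 30 is 7.5, so the limit is exceeded at 8 events: 8/30 = 26.7%; 7/30 = 23.3%. One event is 1/30 = 3.3 percentage points.

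**5. When the limit is applied.** Recruitment is estimated at 12 months and the interim analysis follows 6 months after the last patient. Follow-up at the interim is then about 6 to 6 + 12 = 18 months. Every child is past four scheduled visits (2 and 6 weeks, 3 and 6 months). The gap between years 1 and 2 affects the interim only for children recruited in roughly the first half; the 6-to-12-month gap and drop-out affect it more widely.

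**6. Drop-outs counted as event-free.** The documents give no drop-out rate. For illustration, assume 6 observed refractures and 3 drop-outs who had none when last seen:

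- carried forward as event-free: 6/30 = 20.0%;
- children with known status only: 6/27 = 22.2%;
- all three drop-outs refractured: 9/30 = 30.0%.

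The denominator alone can matter: 7/30 = 23.3% is below the limit, 7/27 = 25.9% is above it.

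**7. Incomplete capture.** The documents give neither a true rate *p* nor a share of events captured *c*; both are assumed. The chance of reaching the limit is P(X ≥ 8) with X binomial (30, *p* × *c*):

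| True rate | c = 100% | 90% | 80% | 70% |
|---|---|---|---|---|
| 10% | 0.008 | 0.004 | 0.002 | 0.001 |
| 20% | 0.239 | 0.158 | 0.095 | 0.050 |
| 25% | 0.486 | 0.358 | 0.239 | 0.141 |
| 30% | 0.719 | 0.585 | 0.435 | 0.285 |
| 40% | 0.956 | 0.898 | 0.792 | 0.632 |

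For example, at a true rate of 30% and 80% capture the expected observed rate is 0.30 × 0.80 = 24%, and the chance of reaching the limit falls from 0.72 to 0.44. At a true rate of 10% the limit is almost never reached whatever the capture; only the reported rate is affected (8% expected at 80% capture). With full capture and no drop-out there is no bias.

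**The case against.** The strongest reply is that the source needed is already authorised. Record access is requested partly to plan and carry out visits and operations, but reading entries and retrieving data is a separate request, and the closing sentence on consent, just before Data security, allows access for carrying out the project and for control. Counting refractures falls within that. The protocol also never says that events come only from the visit list; it keeps reoperated children in follow-up, so it expects reoperations to be known; and the eCRF, which may hold an event item, is not among the documents.

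Most of this stands. A reader might infer that refractures are in fact missed and the rate is in fact too low. The documents do not support that: they give no refracture rate, drop-out rate or capture share, and a complete record search would remove the bias. A reader might also infer that adverse events are not collected at all. That is wrong, as the first table shows. Nor does the contrast of 8 with 7 measure the defect, since one event is decisive at any threshold when the count lies next to it.

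What the reply does not supply is a procedure. Permission to read records is not a plan to search them, and no section says when or for which children this is done. The Bias section's remark that displaced fractures are noticed concerns recruitment; it does not bring a later refracture into the dataset, particularly as the Recruitment section shows that children may first be seen at local clinics or another hospital. The expectation of few missed visits is plausible but does not cover those who do stop.

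**Conclusion.** The point holds as a gap in how events are found. No section states a data item or scheduled search for refracture and reoperation, and the carry-forward rule, applied to refracture, treats a child lost without an event as refracture-free. Under-ascertainment is possible, any resulting bias is downward, and its size cannot be derived from the documents. The figures in steps 6 and 7 rest on assumed rates; they show that the stopping decision is sensitive when the true rate is near or above 25% and hardly at all when it is near 10%. The 25% limit is stated with the interim analysis, so the effect on that decision comes from events up to then; later missed events affect the two-year estimate. The change is worth making because it is cheap and protects the main safety result.

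**What to change.** 1. Add one dated item at every visit, and ask it in the existing missed-visit phone call: *since the last visit, any refracture, reoperation or unscheduled contact for this arm, here or elsewhere (yes/no, date)*. State the study's definition of refracture beside it; the protocol gives none.
2. At the interim and two-year analyses, search the EHR and imaging of every operated child whose consent stands, including those no longer attending, for refracture and reoperation. Count events from all sources.
3. Do not carry the last examination forward for refracture. Report children of unknown status separately, with the denominator stated, and not as refracture-free.

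Cost: one eCRF item and about 30 record look-ups at each of two time points, about 60 in all, under access already sought. No visit, radiograph or treatment changes. The reported refracture rate may be less favourable, and events treated elsewhere will still depend on the parents' report.
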